8.2. Subject disposition

The study has four times of evaluation after baseline: Visit 2 (Day 7), Visit 3 (Day 14), Visit 4 (Day 21), and Visit 5 (Day 28). At each of these times, the disposition of all subjects will be listed and summarized by treatment group. Tables will present the number and percentage of subjects who were screened, randomized, received treatment, or withdrew from the study early by treatment group and overall. For subjects who were randomized but withdrew from the study early, the number and percentage withdrawing by reason will be presented by treatment group and overall.

The Case Report Form (CRF) lists the following reasons why subjects may discontinue treatment before completing of the study:

[figure not shown]
- Adverse event (AE) or serious adverse event (SAE)
- Protocol deviation
- Administrative reason (e.g.: inability to continue, lost to follow-up)
- Sponsor termination of study
- Voluntary withdrawal or withdrawal of consent

In addition, a subject may be discontinued for any sound medical reason at the discretion of the Investigator.

8.3. Treatment exposure

Duration of exposure to study treatment, in weeks, will be summarized for all randomized subjects. Summary statistics for duration of exposure will be presented by visit and treatment group.

8.4. Concomitant medications and therapies

9. Baseline, post-baseline, and unscheduled measurements

Baseline is defined as the last non-missing measurement prior to randomization (Visit 1).

Unless otherwise specified, if a subject has more than one baseline value, the value recorded closest to the date and time of randomization prior to the first dose of study treatment will be used as the baseline measurement.

The clinical study report (CSR) will include listings of all repeated measurements collected prior to first dose indicating whether they were included in the calculation of baseline.

If a laboratory result is retested and the laboratory subsequently considers the original result valid, the original result will be used and the second (i.e., 'retested') result will be ignored. Otherwise, if the laboratory detects an error through the retesting, the retested result will be used as the scheduled measurement and the original result will be ignored.

For post-baseline measures, specific time points will be calculated relative to randomization, rather than solely on the visit labels in the clinical database.

Results of unscheduled tests will be presented in data listings, but they will not be included in summaries of safety for the analysis of change in STS unless otherwise specified.

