9.4.2 Unscheduled Visits

These visits may be performed in order to ensure subject safety. All procedures performed at an unscheduled visit will be recorded in the source documents and on the Unscheduled Visit

eCRF pages. Any procedure indicated in the eCRF that is not performed should be indicated as “Not done.”

Evaluations that may be conducted at an Unscheduled Visit include:

- Slit-lamp Biomicroscopy;
- Visual Acuity;
- Intranasal Examination;
- Urine Pregnancy Test (if applicable);
- Assessment of AEs;
- Assessment of concurrent medications and/or treatments; and
- Any other assessments needed in the judgment of the investigator.

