11.4.5 Secondary Efficacy Analysis

11.4.6 Other Efficacy Analysis

11.4.7 Safety Analysis

All safety analyses will be performed on the safety population.

The safety of OC-02 will be assessed primarily by the incidence of AEs. An AE will be considered a treatment-emergent AE (TEAE) if it occurs or worsens on or after initiation of treatment. An overall summary of TEAEs will be presented including the number of events

and the number of subjects with events (along with percentages) by treatment group for TEAEs in several categories base on seriousness, relationship to treatment, and severity.

Other safety endpoints including visual acuity, slit-lamp biomicroscopy and intranasal examination will be summarized by treatment group and visit using descriptive statistics. Changes or shifts from baseline will be summarized where appropriate. For assessments performed by eye, study eye and fellow eye will be summarized separately. In addition, shifts from baseline to worst on-treatment value for ocular safety assessments will be summarized.

The SAP will present methods of analysis of these defined parameters in detail.

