The examiner should instill 5 μ L of 2% preservative-free sodium fluorescein solution into the inferior conjunctival cul-de-sac of each eye. Alternatively, corneal staining can be assessed using 1.0 mg sodium fluorescein strips. After moistening the tip of the strip with sterile buffered saline, the excess is shaken into a waste bin with a sharp flick. The lower lid is then pulled down and the flat end of the tip should be gently applied to the inferior tarsal conjunctiva with the intent of not inducing reflex tearing and instilling a very small volume of dye.

The participant will be instructed to blink naturally several times without forced closure of the eyelid to distribute the fluorescein. In order to achieve maximum fluorescence, the examiner should wait at least two minutes after instillation before evaluating corneal fluorescein staining. A Wratten #12 yellow filter will be used to enhance the ability to grade fluorescein staining. The staining will be graded with the NEI Scale. The upper eyelid is lifted slightly to grade the entire corneal surface.

Intranasal Examination

Qualified participants for the study must undergo an intranasal exam to make the final eligibility determination (e.g. severe nasal airway obstruction such as, severe septal deviation or inferior turbinate hypertrophy, or vascularized polyp seen on examination are reasons for exclusion). To monitor nasal mucosal integrity during the study for participant safety, an examination of the nasal cavities via an intranasal exam will be performed at the Screening Visit(after all other screening procedures have been completed) and at Visit 5 or the Early Termination Visit. This examination will be performed by an Ear Nose and Throat (ENT) specialist, otolaryngologist or other suitably qualified medical practitioner (i.e. one who has been trained to perform intranasal exam). Still images or video may be captured. The procedure used for the intranasal exam can be conducted either by endoscopic examination or nasal specula.

Schirmer's Test with Topical Anesthesia

At the Screening Visit, one basal Schirmer's test will be performed followed by a Schirmer's test with cotton swab nasal stimulation. The Schirmer's test with topical anesthetic will be used to assess tear production using the following steps:

1. Topical anesthetic drops such as 0.5% proparacaine hydrochloride or equivalent should be instilled in both eyes of the participant.

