3.2. Unscheduled visits

Unscheduled visits may be performed to ensure safety of the subject. The study investigator or designee should record all information gathered at unscheduled visits on the Unscheduled Visit/Early Exit Visit pages of the Source Document and corresponding electronic Case Report Form (eCRF). If a randomized subject does not attend a scheduled visit, the eCRF pages for the missed visit will be skipped. All reasonable efforts should be made to schedule subjects for an Exit Visit to complete Exit Procedures.

4. Analysis populations

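### On its plain words, SAP section 9 keeps unscheduled slit-lamp and visual acuity results out of the safety summaries, and the readable SAP omits the protocol's worst on-treatment ocular shift

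*SAP*

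**What the plan says.** **Handling of unscheduled results.** SAP section 9 has two parts. First, "Results of unscheduled tests will be presented in data listings". Second, "they will not be included in summaries of safety for the analysis of change in STS unless otherwise specified".

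**Purpose of the visits.** The documents agree. Protocol 9.4.2: "These visits may be performed in order to ensure subject safety". SAP 3.2: "Unscheduled visits may be performed to ensure safety of the subject". The evaluations that protocol 9.4.2 names for such a visit include slit lamp, visual acuity and intranasal examination.

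**Planned summary.** Protocol 11.4.7 describes acuity, slit lamp and intranasal results by group and visit, with changes or shifts where appropriate. For the eye it adds that "shifts from baseline to worst on-treatment value for ocular safety assessments will be summarized".

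**What the SAP provides.** Sections 9.1.3 and 11 summarize BCVA by visit. Section 9.1.7 gives slit-lamp summaries by visit and shifts from normal to abnormal, but does not say which post-baseline value defines the shift. Section 9.2 covers intranasal results at named time points. None of these sections mentions a worst value or unscheduled exams.

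**Precedence.** The SAP introduction says that the SAP prevails where the two documents are inconsistent on planned analyses.

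**The concern.** A subject who returns between visits because of an eye problem is the subject whom a worst-value shift table is meant to capture. If that visit's result is kept out of the summaries, the table takes the worst of the scheduled results only. A finding that appears and clears between two scheduled exams then leaves the subject shown as unshifted. Because the SAP governs and does not mention a worst value, a programmer working from it could also omit the protocol's table altogether.

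At stake is the count of subjects whose slit-lamp or acuity result worsened on treatment, in a study small enough for one subject to change a percentage visibly.

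**Working it through.** No stated figure needs to be reproduced. The check is a comparison of texts, then a statement of direction and scale.

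1. **What does the exclusion apply to?** The sentence joins safety summaries to the analysis of change in STS. SAP 2.2 makes change in STS the primary efficacy outcome, so the phrase does not parse. It could mean the safety summaries, the STS analysis, or both.
   - *STS only.* The reference to safety would have no function. The rule would also have little to act on: Schirmer's test is not among the evaluations named in protocol 9.4.2 and could enter only through the closing item on other assessments the investigator judges necessary.
   - *Safety summaries, alone or with STS.* Every word of the rule has a use, and the rule covers exams that unscheduled visits are expected to produce. This is the better reading, though not a certain one.

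2. **Is the exception clause used?** SAP 9.1.3, 9.1.7 and 11 are readable on these exams, and none brings unscheduled results back in. Other SAP text is blacked out, so an exception there cannot be ruled out.

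3. **Is the protocol's summary in the SAP?**

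| Assessment | Protocol 11.4.7 | Readable SAP |
|---|---|---|
| Visual acuity | By visit, plus shift to worst on-treatment value | By visit (9.1.3, 11) |
| Slit lamp | By visit, plus shift to worst on-treatment value | By visit, plus normal-to-abnormal shifts; no worst-value rule (9.1.7) |
| Intranasal exam | By visit, shifts where appropriate; no worst value | Named time points, with shifts (9.2) |

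The two ocular rows differ between the documents. The intranasal row contains no worst-value promise.

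4. **Direction.** Let S be a subject's scheduled post-dose results and U the unscheduled ones. With higher meaning worse (logMAR, or normal < abnormal not clinically significant < abnormal clinically significant), max(S) ≤ max(S ∪ U). The number of subjects shifted using S alone therefore cannot exceed the number using S and U. This holds within each arm. The effect on the difference between arms depends on which arm has such visits.

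5. **Scale.** Planned arm sizes (protocol 6.1) are about 30 on OC-02 and 15 on placebo. One subject is 1/30 = 3.3% or 1/15 = 6.7%. An expected number would require the rate of unscheduled eye exams and the share showing a finding absent from scheduled exams. The documents give neither.

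**The case against.** The strongest reply is that one badly built sentence is being read in its worst sense. It may have been meant only to protect the STS analysis. It carries an exception clause, and the protocol's explicit worst-value summary might count as such an exception, since SAP precedence applies only where the documents conflict. Protocol 11.4.7 assesses safety primarily through adverse events, and protocol Appendix 2 asks that a logMAR increase of 0.22 or more from screening be evaluated as a potential adverse event. SAP section 11 lists all recorded safety parameters. Keeping unscheduled results out of by-visit tables is a reasonable convention in itself.

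Much of this stands. The finding would not be lost, because listings and adverse event tables remain. It follows that a reader who infers that these exams cannot reach any safety output goes too far. But neither route corrects a shift table that shows no shift, and the STS-only reading does not supply the missing worst-value summary.

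Two further inferences are not supported:

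- *That a promised worst-value nasal shift is defeated.* Protocol Appendix 2 gives the purpose of the nasal exam as "To monitor nasal mucosal integrity during the study for participant safety", but the worst-value promise in 11.4.7 covers ocular assessments only. Unscheduled nasal exams stay out of the SAP 9.2 summary because that section names its own time points.
- *That early-exit exams are dropped too.* SAP 3.2 says that staff "should record all information gathered at unscheduled visits on the Unscheduled Visit/Early Exit Visit pages". A shared page name does not show that the two visit types cannot be told apart. Early termination has its own procedure list in protocol 9.3.1 and its own schedule column, and SAP 9.2 includes it for the nasal exam.

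**Conclusion.** The point holds for ocular safety assessments. On its plain words, SAP section 9 leaves safety-prompted slit-lamp and acuity results out of the safety summaries, and the readable SAP does not contain the worst-value shift that protocol 11.4.7 plans. If the SAP is followed as written, an abnormality seen only at an unscheduled visit may go uncounted in a shift table. Any error in an arm's count is downward.

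The size is unknown. The figures of 3.3% and 6.7% show what one subject is worth in each arm; they are not an expected effect. The conclusion assumes that the sentence reaches safety summaries at least in part and that no exception sits in blacked-out text. If the sentence was meant for STS alone, it still needs rewriting, and the worst-value summary is still missing from the readable SAP. This should be corrected, but it does not threaten the primary analysis.

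**What to change.** 1. Split the sentence in SAP section 9. Suggested text: *By-visit summaries and the analysis of change in STS use scheduled visits only. Unscheduled results are listed and also contribute to the worst on-treatment shifts.*
2. In SAP 9.1.3 and 9.1.7, or in section 11, add the baseline-to-worst on-treatment shift for BCVA and slit lamp, by study and fellow eye, using all results after the first dose, including unscheduled and early-termination exams.
3. Optionally, let unscheduled nasal exams enter the shift summary in SAP 9.2. This would be an addition, since the protocol promises no worst-value nasal shift.

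The cost is SAP wording and one derived worst-value record per subject, eye and assessment. No new data are needed. A small downside is that subjects with extra visits have more chances to show a worse value. Reporting the number of subjects with unscheduled eye exams by arm beside the table would let readers judge this.

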9.1. Ocular assessments

Ocular assessments, which will occur at baseline and each study visit, collect results in terms of grade, clinical significance, and relatedness to administration procedure and study drug. These results will be listed, summarized in tables, and presented in figures as appropriate.

9.1.1. Schirmer's Test

The Schirmer's Test with topical anesthetic will be used to assess tear production. At Visit 1, the first Schirmer's Test, which should be performed after corneal fluorescein staining, will be used as the baseline Schirmer's Test score. A second Schirmer's Test with nasal stimulation using cotton swab will occur 10 minutes after the first Schirmer's Test. An additional Schirmer's Test with topical anesthetic will be assessed after the first treatment at Visit 1. At Visits 2, 3, and 5, the Schirmer's Tests will be performed concurrent with treatment.

9.1.2. Eye Dryness Score

The Eye Dryness Score (EDS) will be assessed using a Visual Analog Scale (VAS). EDS scoring is performed by subjects at Visit 1 (baseline), Visit 4 (pre-CAE®), Visit 4 (pre-treatment CAE® exposure, post-treatment CAE® exposure every 5 minutes within the CAE® for a total of 120 minutes), and Visit 5. Participants will be asked to rate their ocular symptoms (both eyes simultaneously) due to eye dryness every 5 minutes during CAE® exposure. At Visit 4, EDS from multiple time points and change in EDS from pre- to post-treatment will be collected and summarized by CAE® exposure period and by treatment group. [REDACTED]

[REDACTED]

9.1.3. BCVA

Visual function of the study and fellow eye will be assessed using the best corrected ETDRS protocol starting at 10 feet. Visual acuity examiners must be certified to ensure consistent measurement of BCVA. In order to provide standardized and well-controlled assessments of

visual acuity during the study, all visual acuity assessments at a single site must be performed consistently using the same lighting conditions and same correction, if possible, during the entire study. If the same correction cannot be used (e.g., a subject broke his/her glasses), the reason for the change in correction should be documented. BCVA will be summarized by visit and by treatment group for both study and fellow eyes.

9.1.4. [REDACTED] Ocular Discomfort Scale

Participants will grade themselves on the [REDACTED] Ocular Discomfort Scale (ODS) with scores from 0 to 4 to indicate the level of discomfort: 0 corresponds to "No discomfort", 1 to "Intermittent awareness", 2 to "Constant awareness", 3 to "Intermittent discomfort", and 4 to "Constant discomfort". The ODS collected at Visit 4 will be used to determine treatment administration. Treatment of investigational drug or placebo will be administered upon a participant's reporting an ODS ≥ 3 at two or more consecutive time points in at least one eye during CAE[®] exposure (participants with an ODS of 3 at time 0 for an eye must report an ODS of 4 for two consecutive measurements for that eye) using [REDACTED] Scale. ODS will be summarized by visit, pre-CAE[®] and every 5 minutes in CAE[®] at Visit 4, and treatment group for both the study and fellow eye.

9.1.5. Ocular Surface Disease Index[®]

The Ocular Surface Disease Index[®] (OSDI[®]) will be collected at screening. The protocol provides the questionnaire, calculation, and details of categorization. The OSDI[®] score will be summarized by treatment with quantitative descriptive statistics (n, mean, median, standard deviation, 25th quartile, 75th quartile, minimum, and maximum).

9.1.6. Corneal Fluorescein Staining

Corneal fluorescein staining will be assessed for both the study and fellow eye. Staining will be graded using the National Eye Institute (NEI)/Industry Workshop Scale. Examiners will score each of five areas on the cornea of each eye: 1 – Central; 2 – Superior; 3 – Temporal; 4 – Nasal; 5 – Inferior. A standardized grading system of 0-3 will be used for each of the five areas. The corneal fluorescein staining score will be described by visit, treatment, study eye, and

fellow eye with summary statistics. Specifically, scores will be presented by each of the five cornea areas and total scores for all corneal areas.

9.1.7. *Slit Lamp Biomicroscopy*

[figure not shown]
A slit lamp will be used for external examination and biomicroscopy. The eyelids, cornea, conjunctiva, anterior chamber, iris, and lens will be examined at each visit. Slit lamp biomicroscopy results will be summarized for each treatment group for the study and fellow eye by visit using discrete summary statistics. Abnormal clinically significant findings will be described. Shifts from baseline including normal to abnormal (not clinically significant), and normal to abnormal (clinically significant) will be presented using counts and percentages.

9.2. *Intranasal assessments*

[figure not shown]
Intranasal assessments collected at the screening visit, the post-treatment CAE® evaluation at Visit 4, and the early termination visit will be summarized by treatment group with counts and percentages. Shifts from baseline of normal to abnormal (not clinically significant) and normal to abnormal (clinically significant) will be presented using counts and percentages.

10. *Efficacy analyses*

10.1. *Primacy efficacy analysis*

[figure not shown]

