least one eye during CAE® exposure (participants with an Ocular Discomfort rating of 3 or 4 at time = 0 for an eye must report an Ocular Discomfort rating of 4 for two consecutive measurements for that eye) using the [REDACTED] Scale. Participants will resume symptom assessments every 5 minutes starting 1 minute after the application ends.

Post-Treatment CAE® Evaluation

- EDS (visual analog scale)
- [REDACTED] Ocular Discomfort Scale
- BCVA (at investigator's discretion as needed)
- Slit lamp biomicroscopy (at investigator's discretion as needed)
- AE Query

Visit 5 (Day 28 ±2): Schirmer's Test Evaluation

- BCVA (pre-and post-treatment)
- Slit lamp biomicroscopy (pre-and post-treatment)
- Intranasal examination
- Administration of study drug/placebo
- Corneal fluorescein staining (post-treatment)
- Schirmer's Test (concurrent with treatment)
- EDS (visual analog scale; post-treatment)
- Concomitant Medications
- AE Query

Early Termination (if applicable)

- BCVA
- Slit lamp biomicroscopy
- Intranasal examination
- Urine pregnancy test (if applicable)
- Concomitant Medications
- AE Query

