This statistical analysis plan (SAP), which is based on Amendment 1.0 of the study protocol dated 11 July 2018, defines the methods and analyses that Oyster Point Pharma, Inc, (henceforth, Oyster Point) plans to use to analyze the data from Protocol OPP-003. This SAP complies with guidance promulgated by the International Conference on Harmonization (ICH) and the US Food and Drug Administration (FDA). If the protocol is subsequently amended, this SAP may be amended as well. Should the SAP and the protocol be inconsistent with respect to the planned analyses, the language of the SAP is governing.

2. Investigational plan

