2.2. Study objectives and outcome measures

The Protocol OPP-003 is designed to evaluate the safety and efficacy of 2.0% OC-02 nasal spray compared to placebo in subjects with DED. See Table 1 for the study objectives and outcome measures.

Table 1. Study objectives and outcome measures

Primary

Objective: to determine if 2.0% OC-02 is superior to placebo with respect to change from baseline in Schirmer's Test Score (STS) at Visit 5 (Day 28)

Outcome: change in STS from baseline to Visit 5

Exploratory & Safety

Objective 1: to evaluate the difference in efficacy between 2.0% OC-02 and placebo with respect to [REDACTED]

[REDACTED]

Objective 2: to compare the safety and tolerability of 2.0% OC-02 nasal spray and placebo with respect to the following outcomes:

- Change in best corrected visual acuity (BCVA)
- Slit-lamp biomicroscopy
- Intranasal examination
- Adverse events

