4.2. Safety population

The safety population will include all randomized subjects who received at least one dose of the study drug. Analysis using the safety population will group subjects according to the treatment actually received. The safety analysis will not exclude any data because of protocol violations.

[figure not shown]
5. Sample size determination and power calculation

The study will randomize approximately 45 subjects in a 2:1 ratio to the two treatment groups. Approximately 28 subjects of the 30 subjects in the 2.0% OC-02 treatment group and 13 of the 15 subjects in the placebo (OC-02 vehicle) nasal spray are expected to complete their assigned treatment and have endpoint assessments at Visit 5.

The primary hypothesis underlying the study is that 2.0% OC-02 nasal spray is superior to the placebo group with respect to mean change in STS from baseline to Visit [REDACTED]
[REDACTED]

6. Protocol deviations

CONFIDENTIAL

Prior to database lock, masked members of study team will review the data for each subject to assess whether an important deviation has occurred. The data management plan will describe the process planned for those reviews.

7. Statistical analysis: general considerations and conventions

Descriptive and inferential statistics will be used to summarize results of Protocol OPP-003.

Continuous variables will be summarized using the number of subjects (n), mean, SD, median, 25th and 75th percentiles, and minimum and maximum. Discrete variables will be summarized using counts and percentages. Baseline measures will be defined as the last measure prior to the initiation of study treatment, usually at Visit 1 screening.

All summaries will be presented by treatment group. Summaries will be provided for demographics, medical history, concomitant medications, and subject disposition. For the summaries of medical history, concomitant medications, and AEs, Medical Dictionary for Regulatory Activities (MedDRA®) and World Health Organization Drug dictionaries, as appropriate, will be used.

All data listings, summaries, and statistical analyses will be generated using SAS® Version 9.4 or higher or other validated software.

The following sections describe the analyses to be used for the study.

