10.2.2. Exploratory efficacy analysis methods

11. Safety analyses

The safety population will be used for all safety analyses. All recorded safety parameters will be listed.

The investigator will promptly review each Adverse Event (AE) for accuracy and completeness, and classify each AE according to its intensity, its relationship to study drug or administration procedure, and its seriousness. AE will be coded using version 20.1 or later of the MedDRA dictionary. AEs will be monitored throughout the study and documented on the appropriate AE form. AEs will be categorized as ocular and non-ocular as well as by system organ class (SOC) and preferred term (PT), seriousness, severity, and relation to study medications. AEs will be summarized by subject, not event.

All AE presentations will summarize treatment-emergent adverse events (TEAEs) defined as AEs with onset on or after first dose of investigational drug or placebo.

The following presentations of AEs will be generated:

- Overall adverse events summary (including any AEs, ocular AEs, resolved ocular AEs, non-ocular AEs, TEAEs, ocular TEAEs, non-ocular TEAEs, SAEs, treatment-emergent SAEs, treatment-related treatment emergent SAEs, TEAEs by maximum severity, TEAEs by relationship to study drug, AEs leading to treatment/study discontinuation);
- Serious adverse events (SAE) by SOC and PT;
- All ocular AEs by SOC and PT;
- All non-ocular AEs by SOC and PT;
- AEs suspected to be related to the study medication;
- AEs leading to treatment discontinuation.
- AEs leading to study discontinuation.

All AE data will be presented in listings. Selected AEs will be listed for ocular TEAEs, AEs leading to treatment discontinuation, AEs leading to study discontinuation, and AEs related to the study medication. In addition, for the safety population “traffic light” plots will present reported AEs by severity over time by treatment group.

BCVA will be summarized by treatment group and study visit for both study and fellow eyes.

12. Subgroup analysis

13. Appendices

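### SAP 9.2 summarises the intranasal examination at Visit 4, where the protocol text schedules none, and omits Visit 5, so read literally the by-arm summary has no end-of-treatment nasal result for expected completers

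*SAP*

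**What the plan says.** SAP 9.2 names the time points for the nasal safety summary: "Intranasal assessments collected at the screening visit, the post-treatment CAE® evaluation at Visit 4, and the early termination visit will be summarized" by treatment group, as counts and percentages. A second sentence plans shifts from baseline (normal to abnormal, split by clinical significance) and names no visit.

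The protocol puts the examination elsewhere:

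- **Protocol 9.3.1** lists "Intranasal examination" under Visit 1, Visit 5 and Early Termination. The three Visit 4 lists (before the CAE, in the CAE before treatment, in the CAE after treatment) do not include it.
- **Protocol Appendix 2, Intranasal Examination**, schedules it at screening "and at Visit 5 or the Early Termination Visit". It gives the purpose as monitoring the integrity of the nasal mucosa.

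On the analysis, Protocol 11.4.7 states: "Other safety endpoints including visual acuity, slit-lamp biomicroscopy and intranasal examination will be summarized by treatment group and visit using descriptive statistics". SAP section 1 states: "Should the SAP and the protocol be inconsistent with respect to the planned analyses, the language of the SAP is governing".

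SAP Table 1 makes intranasal examination one of the outcomes of Objective 2, which is "to compare the safety and tolerability of 2.0% OC-02 nasal spray and placebo with respect to the following outcomes".

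**The concern.** SAP 9.2 names a visit at which the protocol text schedules no examination and leaves out the only scheduled end-of-treatment examination for a subject who completes the study. A table programmed to that sentence would have a Visit 4 column with nothing to fill it and no Visit 5 column.

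The product is sprayed into each nostril twice daily for four weeks, so the nasal examination is the direct look at the site of application. If Visit 5 is left out, the by-arm comparison at the end of treatment rests on the few subjects who stop early. They are a small and selected group, and some may have stopped because of local effects. If the omission is noticed only after unmasking, adding Visit 5 becomes an avoidable departure from the SAP.

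**Working it through.** **1. Visits side by side (prose only)**

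| Time point | Protocol 9.3.1 | Protocol Appendix 2 | SAP 9.2 summary |
|---|---|---|---|
| Screening / Visit 1 | yes | yes | yes |
| Visit 4, post-treatment CAE | no | no | **yes** |
| Visit 5 (Day 28) | yes | yes | **no** |
| Early termination | yes | yes | yes |

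The only post-baseline time point that appears both in SAP 9.2 and in the protocol text is early termination.

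**2. Does anything else bring Visit 5 back?**

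- Protocol 11.4.7 would, through its by-visit summary, but the precedence clause in SAP section 1 favours SAP 9.2.
- The shift to worst on-treatment value in Protocol 11.4.7 is limited to ocular assessments, so it does not cover nasal findings.
- SAP section 11, apart from adverse events, names only a BCVA summary.
- BCVA (SAP 9.1.3) and slit lamp (SAP 9.1.7) are summarised by visit, which takes in Visit 5. The intranasal examination has a fixed list of visits instead.
- The schedule tables (Appendix 1 of each document) have unreliable columns in the text available here. They neither confirm nor refute the point, and nothing below relies on them.

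**3. Number of subjects affected**

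Inputs, from SAP section 5: about 45 randomised 2:1, and "Approximately 28 subjects of the 30 subjects in the 2.0% OC-02 treatment group and 13 of the 15 subjects in the placebo" expected to complete and have Visit 5 assessments.

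- Split: 45 × 2/3 = 30 and 45 × 1/3 = 15, which matches the SAP.
- Expected completers: 28 + 13 = 41; 41/45 = 91.1%. By arm: 28/30 = 93.3% and 13/15 = 86.7%.
- Expected non-completers: 30 − 28 = 2 and 15 − 13 = 2, so 4 in all; 4/45 = 8.9%.

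The 4 is about the most that could contribute an early-termination examination. It falls if some of them do not attend an exit visit.

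**4. What that does to the information in the summary (illustration only)**

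Assume no abnormal shift is seen. The exact one-sided 95% upper limit for zero events in n subjects is 1 − 0.05^(1/n).

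| End-of-study results in the summary | n | Upper limit |
|---|---|---|
| Early termination only, either arm | 2 | 77.6% |
| Visit 5, OC-02 | 28 | 10.1% |
| Visit 5, placebo | 13 | 20.6% |

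The SAP plans no confidence limit for this outcome. The table only shows how little two subjects per arm can exclude.

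**The case against.** The strongest reply is that this is a drafting slip with little consequence. SAP 9.2 does not say that Visit 5 data are excluded, so one can argue that it is silent rather than inconsistent, and that the by-visit plan in Protocol 11.4.7 still applies. The shift sentence in SAP 9.2 names no visit, so it can be read to include Visit 5, and shifts are where treatment-emergent nasal change would show. SAP section 11 adds "All recorded safety parameters will be listed", so Visit 5 results will be visible in any case. Both schedules also mark Visit 1 as pre- and post-treatment, so a Day 1 post-dose result may exist. And because the SAP schedule row cannot be read reliably, a Visit 4 examination may have been intended.

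Much of this stands as a limit on the consequence. The shift table may include Visit 5, the listings will, and the section 5 figures are approximate expectations, so two per arm is not a strict bound. It does not remove the defect. A listing is not a between-arm summary, and a Day 1 result says nothing about four weeks of dosing. The shift sentence leaves Visit 5 to the programmer's reading. A fixed list of visits that includes a wrong one is more than silence, and the SAP gives itself precedence. If a Visit 4 examination was intended, the protocol's procedure lists do not provide for it, and Visit 5 would still be missing from the summary.

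**Conclusion.** The concern holds. SAP 9.2 and the protocol text disagree on when the intranasal examination takes place, and as written the SAP's by-arm summary leaves out end-of-treatment nasal findings for about 41 of 45 subjects (91.1%).

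This rests on three things: a literal reading of SAP 9.2, the approximate completion figures in SAP section 5, and the prose rather than the schedule tables. The gap lies in the by-arm summary, and in the shift table if that is built on the same visits. It should be fixed before database lock, because it affects a named safety outcome at the site of application. Confidence in the mismatch is high.

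**What to change.** In SAP 9.2:

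- Replace the reference to the Visit 4 post-treatment CAE evaluation with Visit 5 (Day 28).
- State that both the summary and the shift-from-baseline table cover screening, Visit 5 and early termination.
- Show Visit 5 and early termination separately, so that completers and early leavers are not pooled.

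Then check the intranasal row of SAP Appendix 1 against Protocol 9.3.1 and Protocol Appendix 2, including whether the pre- and post-treatment mark at Visit 1 is intended. If that check shows that a Visit 4 examination was planned, the two documents must be reconciled on it, and Visit 5 still has to be named.

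The cost is one sentence in the SAP and one table shell. The protocol already collects the data.
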